11.2.1 Serious Adverse Experience Reporting

All SAEs that occur (whether or not related to study drug) will be reported per UCLA OHRPP IRB guidelines and policy. The collection period for all SAEs will begin after informed consent is obtained and end after procedures for the final study visit have been completed.

In accordance with the standard operating procedures and policies of the local Institutional Review Board (IRB), the site investigator will report SAEs to the IRB and FDA.

11.3 Adverse Events of Special Interest

An AESI is an AE (serious or nonserious) of scientific and medical topic of interest, for which ongoing monitoring and immediate notification by the investigator is required and documentation is in the form of a case narrative. Such events may require further investigation to characterize and understand them. Refer to Appendix 2 for a list of AESIs pertinent to this study. All AESIs will be collected through the entire

study period and must be reported immediately and in all circumstances within 7 days of becoming aware of the event. AESIs were identified as immunologically driven sequelae of COVID-19 and thus topics of interest/AESIs for all COVID vaccines.

Anaphylaxis

All suspected cases of anaphylaxis should be recorded and reported as an SAE and AESI, based on criteria for a medically important event, unless the event meets other serious criteria. For reporting purposes, a participant who displays signs/symptoms consistent with anaphylaxis as shown below should be reported as a potential case of anaphylaxis. This is provided as general guidance for investigators and is based on the Brighton Collaboration case definition (27).

Anaphylaxis is an acute hypersensitivity reaction with multi-organ-system involvement that can present as, or rapidly progress to, a severe life-threatening reaction. It may occur following exposure to allergens from a variety of sources. Anaphylaxis is a clinical syndrome characterized by:

1. Sudden onset AND
2. Rapid progression of signs and symptoms AND
3. Involving 2 or more organ systems, as follows:
 - a. Skin/mucosal: urticaria (hives), generalized erythema, angioedema, generalized pruritus with skin rash, generalized prickle sensation, red and itchy eyes
 - b. Cardiovascular: measured hypotension, clinical diagnosis of uncompensated shock, loss of consciousness or decreased level of consciousness, evidence of reduced peripheral circulation
 - c. Respiratory: bilateral wheeze (bronchospasm), difficulty breathing, stridor, upper airway swelling (lip, tongue, throat, uvula, or larynx), respiratory distress, persistent dry cough, hoarse voice, sensation of throat closure, sneezing, rhinorrhea
 - d. Gastrointestinal: diarrhea, abdominal pain, nausea, vomiting

Acute Myocarditis and/or Pericarditis

All suspected cases of probable or confirmed myocarditis, pericarditis, or myopericarditis should be recorded as an AESI, and reported as an SAE, if the event meets seriousness criteria. As an SAE, the event should be reported immediately and in all circumstances within 72 hours. The investigator will submit any updated myocarditis, pericarditis, or myopericarditis case data within 72 hours of it being available. For reporting purposes, a participant who displays signs/symptoms consistent with the CDC case definitions as described below (27), should be reported as a potential case of confirmed or probable myocarditis, pericarditis, or myopericarditis.

The CDC case definitions are intended to serve as a guide to help in the diagnosis and reporting of suspected cases of myocarditis and/or pericarditis; however, the diagnosis of suspected cases is left to the investigator's clinical judgement.

Acute Myocarditis Case Definition

Presence of ≥ 1 new or worsening of the following clinical symptoms (persons who lack the listed symptoms but who meet other criteria may be classified as subclinical myocarditis [probable or confirmed]):

1. Chest pain/pressure/discomfort

2. Dyspnea/shortness of breath/pain with breathing
3. Palpitations
4. Syncope

AND

For PROBABLE CASE:

Presence of ≥ 1 new finding of the following:

1. Troponin level above upper limit of normal (any type of troponin)
2. Abnormal electrocardiogram (ECG or EKG) or rhythm monitoring findings consistent with myocarditis

To meet the ECG or rhythm monitoring criterion, a probable case must include at least one of the following:

- a. ST segment or T-wave abnormalities
- b. Paroxysmal or sustained atrial, supraventricular, or ventricular arrhythmias
- c. AV nodal conduction delays or intraventricular conduction defects

3. Abnormal cardiac function or wall motion abnormalities on echocardiogram

4. Cardiac magnetic resonance imaging (cMRI) finding consistent with myocarditis (28).

AND

1. No other identifiable cause of the symptoms and findings

For CONFIRMED CASE:

1. Histopathologic confirmation of myocarditis (using Dallas criteria (29))

OR

2. cMRI findings consistent with myocarditis in the presence of troponin level above upper limit of normal (any type of troponin).

AND

1. No other identifiable cause of the symptoms and findings

Acute Pericarditis Case Definition

Presence of ≥ 2 new or worsening of the following clinical features (30):

1. Acute chest pain (Typically described as pain made worse by lying down, deep inspiration, or cough; and relieved by sitting up or leaning forward, although other types of chest pain may occur)
2. Pericardial rub on examination
3. New ST-elevation or PR-depression on EKG
4. New or worsening pericardial effusion on echocardiogram or magnetic resonance imaging

Myopericarditis Case Definition

Participants who meet criteria for both myocarditis and pericarditis may be described under myopericarditis.

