6.3 Exclusion Criteria

1. Previous documented COVID-19 infection.
2. Use of investigational agents for prophylaxis against COVID-19 within 90 days of the start of the study, including Evusheld monoclonal antibodies.
3. Ongoing therapy for acute cellular or antibody mediated rejection.
4. Intravenous immunoglobulins (IVIG) administration within the prior 3 months or ongoing IVIG therapy.
5. Anaphylaxis or allergic reaction to any prior vaccines.
6. History of anaphylaxis or other significant adverse reaction requiring medical intervention after receipt of a vaccine.
7. Is acutely ill or febrile 24 hours prior to or at the Day 1 visit. Fever is defined as a body temperature $\geq 38.0^{\circ}\text{C}/100.4^{\circ}\text{F}$. Participants meeting this criterion may be rescheduled within the

relevant window periods. Afebrile participants with minor illnesses can be enrolled at the discretion of the investigator.

8. Pregnant or breastfeeding.
9. Has a medical, psychiatric, or occupational condition that may pose additional risk as a result of participation, or that could interfere with safety assessments or interpretation of results according to the investigator's judgment.
10. Known history of hypertension (HTN) with systolic blood pressure (BP) > 180 mm Hg at the Day 1 visit.
11. Known history of hypotension with systolic blood pressure < 85 mm Hg at the Day 1 visit.
12. Bleeding disorder considered a contraindication to IM injection or phlebotomy.
13. Active malignancy diagnosed within previous 4 years (excluding non-melanoma skin cancer).
14. Received a major surgery including lung transplantation in the past 3 months.

Exclusion of Specific Populations:

Because the effects on the fetus are not known, pregnant women will not be eligible for the trial. Women of childbearing potential (<1 year since start of menopause) must utilize a highly effective method of contraception and will be required to have a negative urine or serum pregnancy test within 24 hours prior to the vaccination. Children will not be included in this trial as presently there are no children receiving lung transplantation at UCLA. Should the outcome of this trial be deemed acceptable, additional trials may be initiated, including those in other populations.

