11 ADVERSE EXPERIENCE REPORTING AND DOCUMENTATION

11.1 Adverse Events

An adverse event (AE) is any untoward medical occurrence in a clinical investigation of a participant administered a pharmaceutical product and that does not necessarily have a causal relationship with the treatment. An AE is therefore any unfavorable and unintended sign (including an abnormal laboratory

finding), symptom or disease temporally associated with the administration of an investigational product, whether or not related to that investigational product. Any medical condition that is present at the time that the subject is screened will be considered as baseline and not reported as an AE. However, if the severity of any pre-existing medical condition increases, it will be recorded as an AE.

AEs can be further divided into solicited AEs and unsolicited AEs. Solicited AEs are those for which the study team will specifically query the subject whether they occurred. Unsolicited AEs are those events that the subject report occurring without being queried about the specific event.

A suspected adverse event is one for which there is a ‘reasonable possibility’ that the drug caused the adverse event. A ‘reasonable possibility’ means there is evidence to suggest a causal relationship between the drug and the adverse event, but implies a lesser degree of certainty about causality compared with an adverse event. An unexpected AE is one of a type not identified in nature, severity, or frequency in the current Investigator’s Brochure or of greater severity or frequency than expected based on the information in the Investigator’s Brochure. All AEs will be assessed for severity and relationship to study intervention (Tables 3 and 4). Suspected, Unexpected, Serious Adverse Reactions (SUSAR) is an adverse event where a causal relationship with the study drug is at least possible but not listed in the Investigator Brochure (IB), Package Insert, and/or Summary of Product Characteristics and includes any of the following: suspected AE, unexpected AE and serious adverse experience (SAE). Episodes of myocarditis or pericarditis occurring in temporal association with vaccination will be reported as a SUSAR. Medically attended adverse event (MAAE) is defined as hospitalization, an emergency room visit or an otherwise unscheduled visit to or from medical personnel for any reason.

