Frequency and grade of each solicited AE (local and systemic reactogenicity) will be collected until Day 7 using the FDA Toxicity Grading Scale to be recorded on a daily diary. Frequency and grade of each unsolicited AEs will be collected until Day 30. Frequency of any SAEs, AESIs and MAAEs will be collected until Day 180. After Day 30 through the end of study on Day 180, only SAEs, AESIs and MAAEs will be reported as AEs. All AEs, solicited and unsolicited, will be captured on the appropriate CRF. Information to be collected for AEs includes event description, date of onset, assessment of severity, relationship to study product and alternate possible etiology, date of resolution, seriousness, and outcome. AEs occurring during the study-collection and reporting period will be documented appropriately regardless of relationship. AEs will be followed to resolution or stabilization.

Solicited Adverse Events:

Solicited AEs are anticipated local and systemic AEs for which consistent collection of information is desired. Study clinicians will follow and collect resolution information for any reactogenicity symptoms that are not resolved within 7 days. Solicited AEs (i.e., reactogenicity) will be collected using a daily diary and recorded on the appropriate CRF from the time of the vaccination until 7 days post vaccination (Days 1-7). For this study, solicited AEs will be defined and graded as follows (Tables 3):

Table 3: Solicited Adverse Reactions and Grading

Phase I/II, Open-label Dose-finding Trial of High-Dose mRNA-1273 Booster for Lung Transplant Recipients
Confidential

Reaction	Grade 0	Grade 1	Grade 2	Grade 3	Grade 4
Injection site pain	None	Does not interfere with activity	Repeated use of over-the-counter pain reliever > (greater than) 24 hours or interferes with activity	Any use of prescription pain reliever or prevents daily activity	Requires emergency room visit or hospitalization
Injection site erythema (redness)	< (less than) 25 mm or < 2.5 cm	25 - 50 mm or 2.5 - 5 cm	51 - 100 mm or 5.1 - 10 cm	> 100 mm or > 10 cm	Necrosis or exfoliative dermatitis (severe skin rash causing skin discoloration or peeling)
Injection site swelling/induration (hardness)	< 25 mm or < 2.5 cm	25 - 50 mm or 2.5 - 5 cm	51 - 100 mm or 5.1 - 10 cm	> 100 mm or > 10 cm	Necrosis (severe swelling with skin discoloration, blistering, or peeling)

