APPENDIX 2: ADVERSE EVENTS OF SPECIAL INTEREST (AESI) TERMS

The Investigator's medical judgement must be applied to assess an event as an AESI, as most AESIs are based on medical concepts. The table below does not provide a comprehensive list of terms.

The following table describes events/medical concepts that are of interest in COVID-19 vaccine safety surveillance. Some are specific to vaccines; however, some are of interest due to their occurrence in the context of concurrent or recent COVID-19. Events falling into the descriptions below should be reported as AESIs, per protocol, even when they occur during/following COVID infection.

Please note: COVID-19 itself is not an AESI.

Medical Concept	Medical Concept Descriptions/Guidance
0. Not an AESI	
1. Anosmia, Ageusia	
• New onset of anosmia or ageusia associated with COVID-19 or idiopathic etiology• DOES NOT INCLUDE anosmia or ageusia associated with sinus/nasal congestion, congenital, or traumatic etiologies
2. Subacute thyroiditis	
• Acute inflammatory disease of the thyroid (immune-mediated or idiopathic)• DOES NOT INCLUDE new onset of chronic thyroiditis
3. Acute pancreatitis	
• New onset of pancreatitis in the absence of a clear, alternate etiology, such as alcohol, gallstones, trauma, recent invasive procedure, etc.
4. Appendicitis	
• Any event of appendicitis
5. Rhabdomyolysis	
• New onset of rhabdomyolysis in the absence of a clear, alternate etiology, such as drug/alcohol abuse, excessive exercise, trauma, etc.
6. Acute respiratory distress syndrome (ARDS)	
• New onset of ARDS/respiratory failure due to acute inflammatory lung injury• DOES NOT INCLUDE non-specific symptoms of shortness of breath or dyspnea, nor events with underlying etiologies of heart failure or fluid overload
7. Coagulation disorders	
• New onset of thrombosis, thromboembolic event, or non-traumatic hemorrhage/bleeding disorder (ex. stroke, DVT, pulmonary embolism, disseminated intravascular coagulation (DIC), etc.)

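### Allograft rejection is not listed as an adverse event of special interest, so a non-serious rejection found at a scheduled visit after Day 30 need not be collected

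*Combined protocol and SAP*

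**What the plan says.** **AESI list.** Section 11.3 takes its AESIs from COVID-19 and from topics common to all COVID vaccines ("AESIs were identified as immunologically driven sequelae of COVID-19") and directs the reader onward: "Refer to Appendix 2 for a list of AESIs pertinent to this study". Appendix 2 gives 17 numbered concepts. None names acute cellular rejection, antibody-mediated rejection or chronic allograft dysfunction. The appendix does not present itself as closed: "The table below does not provide a comprehensive list of terms", and "The Investigator's medical judgement must be applied to assess an event as an AESI".

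**Collection windows.** Section 11.1 states: "Frequency and grade of each unsolicited AEs will be collected until Day 30". From then to Day 180, "only SAEs, AESIs and MAAEs will be reported as AEs". The paragraph on unsolicited events, later in section 11.1, is narrower and keeps only SAEs and AESIs. An MAAE is a hospitalization, an emergency room visit or "an otherwise unscheduled visit to or from medical personnel for any reason".

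**Where rejection appears.** It is named in eligibility and concomitant-medication text only. Section 6.3 excludes people with "Ongoing therapy for acute cellular or antibody mediated rejection", and sections 7.1 and 9.1.1 repeat the idea. It is not in the safety endpoints (5.1), the halting criteria (12.2, 12.3) or the schedule of events (Appendix 1).

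**The concern.** The primary objective (3.1) is safety in lung transplant recipients. The trial gives up to 200/50 = 4 times the booster dose that section 2 calls currently recommended, and section 2.1 hypothesises a stronger immune response from the higher doses. By excluding people under treatment for rejection, the protocol already treats rejection as relevant to this population. Appendix 3 adjusts laboratory grades for transplant recipients, and Appendix 1 schedules a review of myocarditis and pericarditis symptoms at every follow-up contact to Day 180. No comparable step is taken for the graft.

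At stake is whether the Day 180 safety tables can be read as covering non-serious graft events. Recording that is left to discretion may also be uneven: the study is open-label, participants are told their dose (10.2), and staff who know the dose might look harder for, or be readier to report, a graft event in one group than in another.

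**Working it through.** The plan states no figure on this point, so the check is mainly a reading of the text.

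**Step 1: trace one event.** Take a rejection judged non-serious, found at a scheduled transplant visit on Day 60 and managed without an unscheduled visit.

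| Category | Rule | Required? |
|---|---|---|
| Unsolicited AE | 11.1: collected to Day 30 | No, window closed |
| SAE | 11.2: listed outcomes, or an important medical event by judgement | No, non-serious by premise |
| MAAE | 11.1: hospitalization, emergency room or unscheduled visit | No, visit was scheduled |
| AESI | Appendix 2: 17 concepts | Not listed; reportable by judgement |

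No category makes collection mandatory. There is little indirect evidence to fall back on. After Day 30 the only scheduled study contacts are two telephone calls (10.6, 10.7), and Appendix 1 records concomitant medications only at Visit 1, so later treatment for rejection would not reveal the event.

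**Step 2: compare the texts on what is recorded after Day 30.**

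| Place | Recorded or reviewed after Day 30 |
|---|---|
| 9.1.6 | AEs, throughout the study |
| 5.3, 10.6, 10.7, Appendix 1 | AEs, SAEs, AESIs and MAAEs, at Days 90 and 180 |
| 5.1 (third endpoint); 11.1, collection windows | SAEs, AESIs, MAAEs |
| Synopsis (third primary endpoint); 11.1, unsolicited AEs | SAEs, AESIs |

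These are three different rules. Under the first two rows a rejection mentioned on a call could be noted. Under the third it is not reported as an AE and does not enter the Day 180 endpoint. Under the fourth, even a non-serious rejection seen at an unscheduled visit drops out.

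**Step 3: time share.** Days outside the unsolicited-AE window: 180 − 30 = 150. Share of follow-up: 150/180 = 83%. This is calendar time, not a share of rejections.

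**Step 4: illustration with assumed rates.** The documents give no rejection incidence, so the 180-day risk p is an assumption, with constant hazard. The 30-day risk is q = 1 − (1 − p)^(30/180). The chance of recording at least one event in an arm of 20 is 1 − (1 − q)^20 with a 30-day window and 1 − (1 − p)^20 with a 180-day window.

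| Assumed p | q | 30-day window | 180-day window |
|---|---|---|---|
| 2% | 0.34% | 6.5% | 33% |
| 5% | 0.85% | 16% | 64% |
| 10% | 1.74% | 30% | 88% |
| 15% | 2.67% | 42% | 96% |

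The gap between the last two columns is an upper bound on the loss. It treats every rejection as non-serious and routinely found, and assumes that nothing is recorded by discretion.

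**The case against.** The strongest reply is that the plan does not shut rejection out after Day 30. Sections 9.1.6, 10.6 and 10.7 and Appendix 1 all speak of AEs being captured or reviewed to the end of the study. Appendix 2 disclaims completeness and calls for medical judgement, and section 11.3 lets an AESI be non-serious. Section 11.2 lets an important medical event be treated as an SAE. Any unscheduled visit makes the event an MAAE under the main text of 11.1, with no admission needed. All AEs are collected to Day 30, and respiratory failure from acute inflammatory lung injury is an AESI to Day 180. The AESI basis is stated openly, so this is a design choice and not an error.

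Most of this stands, and it rules out three readings that a reader might infer:

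- *That a rejection after Day 30 cannot be recorded.* It can be; it does not have to be.
- *That 83% of rejections would be missed.* The documents give neither incidence nor a split by seriousness or mode of detection.
- *That the safety results say nothing about the graft, or that dose affects rejection.* Early and serious events are covered, and no passage offers data on a dose effect.

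The reply does not supply a requirement. The routes through 11.2 and Appendix 2 are permissive, and the Appendix 2 disclaimer may refer only to terms within the listed concepts. The review text in 9.1.6, 10.6, 10.7 and Appendix 1 collides with an explicit limit in 11.1. A collision between sections is a reason to reconcile them, not assurance that the event will be captured.

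**Conclusion.** The point holds in a bounded form. Rejection and chronic allograft dysfunction are not listed as AESIs. An event that is judged non-serious, found at a scheduled visit, managed without an unscheduled one and not elevated by judgement has no mandatory collection in Days 31 to 180. That is 150 of 180 days; the number of events affected is unknown. Under the narrower sentence in 11.1 the gap is somewhat wider, because MAAEs drop out as well.

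This rests on reading the limit in 11.1 as governing over the general review text elsewhere, which the plan does not settle. The text of section 11.4 (Medical Monitoring) was not available for this check; if it requires graft events to be recorded, the point narrows or falls.

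The finding is best classed as a cheap improvement to a safety trial in graft recipients, not as a flaw that invalidates the primary analysis.

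**What to change.** 1. Add one row to Appendix 2: *new or worsening acute cellular rejection, antibody-mediated rejection or chronic allograft dysfunction diagnosed by the treating team*.
2. Collect it from Day 1 to Day 180 at the existing visits, with a chart check at the Day 90 and Day 180 calls, applied identically in all dose groups.
3. Tabulate it descriptively by dose group in the Safety Analysis Set.
4. Reconcile the synopsis, 5.1, 5.3, 9.1.6, 10.6, 10.7, both statements in 11.1 and Appendix 1, so that one rule says which AEs are recorded after Day 30 and whether MAAEs are among them.

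No biopsy, test, halting rule or clinical decision is added. The cost is two chart checks per participant and a few more narratives. With 20 per arm the result is a count by dose, in keeping with the descriptive primary analysis (14.3), and will not support a reliable comparison between doses.

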12 DISCONTINUATION AND REPLACEMENT OF PARTICIPANTS

12.1 Screen Failures

Screen failures are defined as participants who consent to participate in the study but are not subsequently assigned to study intervention. A minimal set of screen failure information is required to ensure transparent reporting of screen failure participants to meet the Consolidated Standards of Reporting Trials (CONSORT) publishing requirements and to respond to queries from regulatory authorities. Minimal information includes demography, screen failure details, eligibility criteria, and any SAE.

After the screening assessments have been completed, the PI or qualified designee is to review the inclusion and exclusion criteria and determine the participant's eligibility for the study. Only the following information will be collected on screen failures: demographics (age, screen number, sex, ethnicity, and race, BMI, medication history, co-morbidities including cardiovascular disease, risk factors for cardiovascular disease, and immunosuppressive agents) and reason for ineligibility. Participants who are found to be ineligible will be told the reason for ineligibility.

